1. ADT

Androgen suppression therapy consists of combined androgen blockade. Patients receive an antiandrogen, typically bicalutamide (Casodex) and an LHRH-agonist, typically Lupron. AST is given for two months prior to radiotherapy and then continued for a total of six to 36 months, depending upon the treating physician and overall health of the patient.

2. PSA

Serum PSA will be checked at baseline by treating physician, prior to commencing therapy. Serum PSA will also be subsequently checked on the same day as each follow-up MR is performed, i.e. TP 1,2 and 3, and right after finishing EBRT.

Parking at BWH for time spent for all 4 follow-up serum PSAs will be paid for.

3. Prostate MRI

The baseline prostate MRI is standard of care management, ordered by the radiation oncologist for staging and for EBRT planning. The 3 follow-up MRIs (at TP 1,2 and 3) are not standard of care management, and will be paid for by an NIH grant. However, all of the follow up prostate MRIs will use a standard BWH Radiology Department prostate non-endorectal coil MRI protocol. Subjects will need, to complete health screening and renal assessment forms completed prior to the MRI to determine if the patient is able to receive gadolinium. Blood results measuring renal function within a 3-week window prior to MR must be available, and if necessary, blood will be drawn to measure kidney function prior to administration of gadolinium. Subjects will be positioned lying on their back within the MRI magnet, which is a large cylindrical tube that allows strong magnetic fields to pass through the body. Earplugs and a padded table will be provided for the subject's comfort. A radio frequency receiver coil encased in a plastic mold called a phased-array coil will be positioned around the subject's pelvis. An endorectal coil will NOT be used for this study, as the endorectal probe will distort the prostate (making correlation with CT for planning difficult) and because of the risk of proctitis during EBRT.

The standard imaging protocol will include fast spin echo (FSE) for T2WI, fast spoiled gradient (FSPGR) for T1WI and (Dynamic Contrast Enhanced) DCE-maps, and diffusion imaging for ADCmaps. If renal function is normal, the MR contrast agent gadopentetate dimeglumine (Magnevist) will be used for DCE. A dose of 0.1 mmol/kg is administered intravenously using an MR compatible power injector immediately before beginning the dynamic contrast enhancement (DCE) portion of the MRI exam. Magnevist is not given to patients with a history of prior allergic reaction, which is extremely rare. Possible use of light sedation for anxiety associated with the MRI exam should be discussed between the patient and referring physician prior to the MRI exam. If any anti-anxiety medication is prescribed, subjects should bring it to the examination and use as directed. Subjects will also be told to take all of their prescribed medications as regularly scheduled.

Parking at BWH for time spent for 3 follow-up prostate MRIs will be paid for.

Following the multiparametric MRI exam, the imaging data will be collected and archived. A standard clinical prostate MRI staging report will be issued in a timely fashion. The quantitative MR-based information (ADC-maps and DCE pharmacokinetics) will be analyzed separately using Oncoquant software (GE Healthcare) and will not be included in the standard MRI report. Should the results of this additional analysis impact the interpretation rendered in the standard prostate report, the referring physician will be contacted and advised. Individual results will not be discussed with or returned to the participating patients.

4. EBRT

Intensity-modulated EBRT will be given using daily pre-treatment imaging on implanted fiducials according to Brigham and Women's standards. This is referred to as image-guided, intensity modulated radiotherapy, or IGRT. The IGRT targets the prostate and seminal vesicles and in some cases, the pelvic nodes as well according to well standardized department protocols. Each daily treatment, or fraction, delivers 1.8 Gy to a total of 75.6 Gy over 42 treatment days. Treatments are given five days per week.

5. Fusion of the CT and 3T MRI images

3Tesla MRI is known to have a superior ability to visualize the prostatic apex and the prostatic rectal interface compared to CT. Therefore we seek to ascertain if the information provided using 3Tesla MRI images can supplement CT information for Radiation Treatment (RT) planning purposes in men who are planning to undergo RT for prostate cancer. This protocol is acquiring 3T MRI images without an endorectal coil in men planning to undergo RT for prostate cancer after fiducial marker placement and CT simulation but prior to the start of RT. We will perform a fusion of the CT and non-endorectal coil 3T MRI images using the intraprostatic fiducial markers. The fusion will allow us to assess if improved delineation of the prostatic apex and prostatic rectal border translates into not losing any target (i.e. prostate gland) coverage but reduces the volume of rectum receiving radiation in excess of 70 Gray. We will use the validated rectal metrics of a rectal V70 < 20% and also <10cc as the measurement to make this assessment. If the rectal V70 can be reduced with MRI information then the risk of late RT induced rectal bleeding would be expected to decrease. The MR data will not be used in the RT treatment planning of these men but only for the assessment of whether the rectal V70 could be reduced.

VII Biostatistics

1. Correlation of ADC Change With PSA Nadir

Zelevsky et al. report that 10-year relapse-free survival among patients with PSA nadir ≤ 0.3 was 74.3%, compared with 57.7% for patients with higher PSA nadir values ($P = 0.001$, $N = 1045$). In order to assess power for a test of whether mpMR parameters measured after 2 months neoadjuvant ADT therapy alone correlate with nadir PSA post 8-weeks of ADT therapy, we will make use of published data on the correlation between ADC change and nadir PSA. Foltz et al.[24] observed a correlation of 0.25 for nadir PSA with ADC percent change, between 6 weeks and the pre-RT baseline ($N = 10$). With 30 subjects, we anticipate 80% power to detect an absolute correlation of 0.49 or greater. Although this is greater than the correlation Foltz observed, we note that with a sample of size 10, using Fisher's transformation, an approximate 95% confidence interval for Foltz's estimate is (-0.45, 0.76), a wide interval which includes 0.49.

2. Within-Patient ADC Changes

Foltz et al.[24] reported a change in ADC between six weeks RT and baseline of -0.29 in tumor (2.8%, N = 36) and -0.56 in healthy tissue (N=10), with SDs of 0.23 and 0.18, respectively (in units of 10^{-3} mm²/s). Using the average variance above, we estimate a SD for ADC of 0.20. With N = 30 subjects, using this SD, we expect to have 80% power to detect a significant within-subject absolute difference in ADC between two time points of 0.14 or greater, based on a paired t-test at the 0.05 twotailed significance level, corrected for the 6 pairs of time points to be considered. This is much smaller than the difference of 0.81 observed in healthy tissue described by Barrett et al.[23], but larger than the very small difference of 0.03 that they observed in tumor. Foltz et al. observed changes in ADC between 4 weeks and baseline of 0.107 (B = 600) and 0.117 (B = 1200), both of which are less than 0.14.

3. Comparison of Normal Tissue ADC With Tumor

For comparisons between tumor and normal tissue, with 30 subjects we expect 80% power to detect an absolute difference in mean ADC of 0.19 or greater, based on a two-tailed two-sample t-test, adjusted for multiple comparison of time-points. Barrett's group observed a mean difference in ADC between tumor and healthy tissue of 0.20.

4. Comparison of ADC Changes between Patients who Fail Treatment and Those who do not.

We estimate that 25% of men with grade T2c or greater cancer will have end PSA greater than 0.5, and will fail therapy. Barrett et al. reported a change in ADC between three months of ADT and a preADT baseline in tumor of -0.028 with a SD of 0.227 (N = 35), in 20 patients with tumor of stage T2c or greater. We therefore estimate that ultimately 25% of these patients failed. We assume that the ADC changes in patients who fail and patients who do not fail are both normally distributed, with the same SD but different means. We estimate this SD from the Barrett et al. data as $0.227/\sqrt{0.25^2+0.75^2} = 0.287$. In our study, with 30 patients, we expect approximately 8 treatment failures. Assuming 8 failures and a SD of 0.287, we will have 80% power to detect an absolute difference between the mean ADC change among those who fail treatment and those who do not of 0.51 SDs, or $0.51 \times 0.287 = 0.15 \times 10^{-3}$ mm²/s change in ADC. Barrett observed a baseline ADC mean in tumor of 1.006, hence we expect to be able to detect a change from baseline and 3-months ADT in ADC of approximately +/- 15% or greater.

5. Descriptive statistics will be used to enumerate the rectal V70's achieved using MRI versus CT data.

VIII Risks and Discomforts

Participants in this study will undergo a total of 3 follow up prostate MRIs. (Baseline standard of care prostate MRI prior to initiating therapy will be ordered by the treating physician). All MRIs will use a standard routine prostate MRI protocol without the use of an endorectal coil. Patients will receive Magnavist 0.1mmol/kg intravenously for each study, so renal function will need to be checked prior to

each study to confirm normal function. If renal function is abnormal, the contrast agent will not be administered. Unlike CT (which uses radiation to produce images), MRI uses powerful magnetic fields and radio waves to produce images. There are no known health risks associated with this exposure. The radio waves used can cause a warming sensation to the body, similar to exposure to hot weather, or localized heating adjacent to the torso coil or ecoil. Body temperature can be expected to rise temporarily, but less than 1° Centigrade or about 2° Fahrenheit. In the event of a localized heating sensation, the subject will be instructed to notify the MR technologist immediately. However, the MRI scanner and the coils used have been designed to prevent localized heating from happening and there have been no reports of localized heating in patients scanned to date.

The MRI scanner also uses rapidly switched magnetic field gradients that make loud banging noises as it collects the information used to create images. Earplugs will be used to reduce this noise and will be offered to each subject. The switched gradients can, under certain circumstances, cause peripheral nerve stimulation that may be experienced as a mild twitching in the limbs and/or lower back muscles. Such effects are rare and scan settings are kept well below the levels where such effects are known to occur.

Subjects will be carefully screened at the time of enrollment to make certain that they do not have any unsafe metal implants. People who feel uncomfortable in confined spaces (claustrophobia) may feel uncomfortable lying in the narrow cylinder of the MRI magnet. Subjects will be able to communicate with the MRI technologist for the entire time they are in the magnet. The MRI will be stopped at the subject's request at any time he so wishes. In addition, all patients will be offered Ativan (.5-1 mg) by their treating radiation oncologist. They also have the option to take a second dose upon arrival if they feel tense. All are driven home by a friend or relative.

IX Potential Benefit

No direct benefits from the study should be expected by individuals participating in this study. Results from this study, however, may indicate that mpMRI is an early non-invasive biomarker that may predict those that will respond to ADT/EBRT and in particular, determine those who may benefit from long-term androgen suppression or use of non-standard hormone therapies that are now being explored in patients with metastatic disease. As mpMRI of the prostate evaluates tumor physiology and functionality within the entire prostate gland, it offers information about underlying tumor heterogeneity and how these tumors respond to ADT alone and in combination with EBRT. The hope is that results from this study may offer preliminary information on how functional evaluation of the entire prostate could aid in strategizing patients for an optimal patient-specific therapy plan.

X Monitoring and QA

All subjects will complete the safety screening form, which will be reviewed by the MRI technician. During the multiparametric MRI exam, the subject will be monitored for safety in the MR environment by the MRI technologist. The quality of the MR data will be monitored by the MRI technologist as it is being acquired and by the study doctors on an ongoing basis.

All patient records will be kept on site and confidential. No individual identifiers will be used in any reports or publications resulting from this study. Data security will be controlled by limiting its electronic transmission and storage using secure networks and protected data archives at Brigham and Women's Hospital.

Standard monitoring software supplied by the manufacturer of the MR scanner will be used to insure compliance with specific FDA guidelines regarding power deposition, gradient slew-rates, and field strength. MRSI quality assurance will be monitored using phantom studies performed within one week prior to any patient study to assure the MR scanner is functioning properly for reproducible data acquisition.

All serious adverse events will be reported directly to the DFCI Office for Human Research Studies(OHRS). These include any serious adverse events such as an untoward medical occurrence that results in death or is life threatening (at the time of the event) or requires inpatient hospitalization or results in persistent or significant disability or incapacity. Expected adverse events from MRI are not serious and include claustrophobia while in the MRI magnet, a warming sensation while in the MRI magnet, or infiltration of intravenous contrast in the subcutaneous tissues at the time of its administration. All reasonable measures will be taken to avoid these adverse events.

XI: Registration with QACT

The registration procedure will be as follows:

1. Obtain written informed consent from the participant prior to the performance of any nonstandard of care prostate MRI.
2. Complete the protocol-specific eligibility checklist using the eligibility assessment documented in the participant's medical/research record. **To be eligible for registration to the study, the participant must meet each inclusion and exclusion criteria listed on the eligibility**
3. Fax the eligibility checklist(s) and all pages of the consent form(s) to the QACT at **checklist**.
[REDACTED]
4. The QACT Registrar will (a) validate eligibility and (b) register the participant on the study
5. The QACT Registrar will send an email confirmation of the registration and/or randomization to the person initiating the registration immediately following the registration and/or randomization.

XII References.

- [1] J. V Hegde, R. V Mulkern, L. P. Panych, F. M. Fennessy, A. Fedorov, S. E. Maier, and C. M.

- C. Tempany, "Multiparametric MRI of prostate cancer: An update on state-of-the-art techniques and their performance in detecting and localizing prostate cancer.," *Journal of magnetic resonance imaging : JMRI*, vol. 37, no. 5, pp. 1035–54, May 2013.
- [2] L. M. Wu, J.-R. Xu, H. Y. Gu, J. Hua, J. Zhu, J. Chen, W. Zhang, and J. Hu, "Role of magnetic resonance imaging in the detection of local prostate cancer recurrence after external beam radiotherapy and radical prostatectomy.," *Clinical oncology (Royal College of Radiologists (Great Britain))*, vol. 25, no. 4, pp. 252–64, Apr. 2013.

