1. The primary endpoint of this study is whether mpMR parameters measured after 2 months of neoadjuvant ADT therapy (TP1) correlate with nadir PSA post 8-weeks of ADT. In addition, we will determine whether mpMR parameters in areas of tumor (T) in those who fail neoadjuvant ADT (defined as PSA end ADT values $>.3$ ng/ml) are different to those who respond to ADT (defined as PSA end ADT $\leq.3$ ng/ml).
2. A secondary endpoint of this study is whether mpMR parameters measured after 6 weeks of EBRT (TP2) and 8 weeks after completion of EBRT (TP3) correlate with end PSA (defined as PSA level immediately after EBRT treatment). In addition, we will determine whether mpMR parameters in areas of T in those likely to fail combined ADT/EBRT (defined as PSA end values $>.5$ ng/ml) are different to those of responders (PSA end values $\leq.5$ ng/ml).

IV Subject selection

1. Inclusion criteria:
 - a. Adult males with unfavorable intermediate- to high-risk localized disease identified as one of the following three categories for unfavorable intermediatehigh risk factors, but must have visible disease on baseline MRI.
 - i. Clinical or radiographic T2b-T4 primary tumor
 - ii. Gleason score 7-10 in any core
 - iii. PSA ≥ 10 prior to initiation of therapy
 - b. Patients are deemed suitable for therapy with ADT and EBRT.
 - c. Subjects must be able to provide informed written consent prior to study entry.
2. Exclusion criteria:
 - a. The standard exclusion criteria for MRI exams will apply which include patients with pacemakers, non-compatible intra-cranial vascular clips, inner ear implants, and severe claustrophobia.
 - b. Patients who because of age, general medical or psychiatric condition, or physiologic status unrelated to the presence of prostate cancer are unlikely to be candidates for repeat MRIs, or cannot give valid informed consent.
 - c. Patients unwilling or unable to undergo the ecoli placement or multiparametric MRI exam.
 - d. Patients with a history of allergic reaction to latex or Gadolinium containing intravenous contrast agents.

- e. Individuals with renal disease or other contraindications to gadolinium will be excluded. The BWH standard MRI contrast screening criteria will be used to establish renal status.
- f. Patients who have had prior prostatectomy or prior androgen therapy.

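### VII.2 gives one detectable ADC change (0.14) from an SD averaged over two tissues; on the quoted SDs, taken as patient-level, the 80% limits are about 0.16 in tumor and 0.12 in healthy tissue

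*Combined protocol and SAP*

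**What the plan says.** Section VII.2 (Within-Patient ADC Changes) cites, from the radiotherapy study, six-week changes in ADC "of -0.29 in tumor (2.8%, N = 36) and -0.56 in healthy tissue (N=10), with SDs of 0.23 and 0.18" (units 10^-3 mm²/s). It combines the two spreads: "Using the average variance above, we estimate a SD for ADC of 0.20". With N = 30, a paired t-test and a two-sided 0.05 level corrected for six pairs of time points, it claims 80% power for a "within-subject absolute difference in ADC between two time points of 0.14 or greater".

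The section does not say which tissue 0.14 refers to. It compares 0.14 with a healthy-tissue change of 0.81 and then, for tumor, calls the limit "larger than the very small difference of 0.03 that they observed in tumor". It adds that two further changes, 0.107 and 0.117, are below 0.14, without naming their tissue.

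Section VII.4 gives figures from the other cited study, on androgen deprivation: a change "in tumor of -0.028 with a SD of 0.227 (N = 35), in 20 patients with tumor of stage T2c or greater", and "a baseline ADC mean in tumor of 1.006".

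**The concern.** A paired t-test of ADC between two time points depends on the SD of the within-patient change in the tissue being tested. VII.2 quotes a different SD for each tissue, uses neither, and applies one limit to both. Comparison of tumor with normal tissue has its own calculation in VII.3, so nothing in VII.2 needs a value common to both tissues.

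The averaged SD is too small for tumor and too large for healthy tissue, if the quoted values are taken at face value. The stated power is then too favorable in tumor, the tissue named in the section III group comparisons, and too cautious in healthy tissue. What is at stake is how a null result is read: a non-significant tumor change would be judged against 0.14 when the limit for that tissue is somewhat higher.

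A second, smaller point sits in the same sentence. The tumor change is printed as -0.29 and as 2.8%, and these do not fit together if the percentage is relative to a baseline near 1.0.

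**Working it through.** **Inputs.** From VII.2: N = 30; two-sided alpha 0.05 corrected for six pairs (the method is not named; Bonferroni is taken here, 0.05/6 = 0.00833); SDs 0.23 (tumor, N = 36) and 0.18 (healthy, N = 10); difference 0.14. From VII.4: tumor SD 0.227, with N = 35 in 20 patients; baseline tumor ADC 1.006. No dropout is assumed.

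**Method.** Noncentral t with 29 df and noncentrality = difference / (SD/√30). The critical value is 2.83. For 80% power, the detectable difference is 0.676 × SD.

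**The plan's figure.** √((0.23² + 0.18²)/2) = √((0.0529 + 0.0324)/2) = 0.2065. The noncentrality is 0.14/(0.2065/√30) = 3.71, the power is 80.2%, and the 80% limit is 0.676 × 0.2065 = 0.140. The plan's statement reproduces. With the printed 0.20, power is 83.2% and the limit 0.135, which still rounds to 0.14.

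**By tissue, taking the SDs as patient-level SDs of change.**

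| SD | Source | Noncentrality at 0.14 | Power at 0.14 | 80% limit |
|---|---|---|---|---|
| 0.23 | VII.2, tumor | 3.33 | 69.0% | 0.156 |
| 0.227 | VII.4, tumor | 3.38 | 70.4% | 0.154 |
| 0.18 | VII.2, healthy | 4.26 | 91.3% | 0.122 |

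**Precision of the SDs (chi-square 95% limits).**
- Tumor, 35 df: SD 0.187 to 0.300, limit 0.13 to 0.20, power at 0.14 from 89% down to 41%. This treats the 36 observations as independent.
- Healthy, 9 df: SD 0.124 to 0.329, limit 0.08 to 0.22.

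**Unit of analysis.** VII.2 does not say whether 36 counts lesions or patients. VII.1 gives N = 10 for a correlation from the same study, and VII.4 shows more observations than patients in the other one. Assume that 0.23 is per lesion and that a patient's value is the mean of m lesions with within-patient correlation ρ. The patient-level SD is then 0.23 × √((1 + (m − 1)ρ)/m). With m = 35/20 = 1.75, borrowed from the other study:

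| ρ | SD | 80% limit | Power at 0.14 |
|---|---|---|---|
| 0 | 0.174 | 0.118 | 93% |
| 0.5 | 0.204 | 0.138 | 81% |
| 1 | 0.230 | 0.156 | 69% |

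Under that assumption the stated 80% at 0.14 holds if ρ is at most 0.55 (at most 0.73 if the 36 came from 10 patients, m = 3.6). With one lesion per patient, 69% applies.

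**Against the cited changes.** 0.03, 0.107 and 0.117 lie below 0.122, 0.14 and 0.156 alike; 0.29, 0.56 and 0.81 lie above all three.

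**The tumor change.** Read as a percent of baseline, -0.29 and 2.8% imply a baseline of 0.29/0.028 = 10.4 (10.0 to 10.7 allowing for rounding). Against 1.006, which comes from the other study and is used here as an assumption, 0.29 is 28.8%, and 2.8% is 0.028. For assumed baselines of 0.8 to 1.5, 0.29 is 36% to 19%.

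**The case against.** The strongest reply is that there is no arithmetic error. The plan discloses that it averaged the variances, and its result follows. That stands: the issue is the choice of input, and a reader who infers a miscalculation would be wrong.

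Second, the two SDs are not clearly different. If the observations are independent, F = 0.0529/0.0324 = 1.63 on 35 and 9 df, two-sided p = 0.44, and both ranges above contain 0.14. This limits how firmly 0.156 can be preferred to 0.140. The test is weak with ten healthy-tissue observations, however, and pooling by degrees of freedom would give an SD of 0.221, a limit of 0.149 and 73% power at 0.14, not 80%.

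Third, 69% is only one case. It needs 0.23 to be a patient-level SD, and under lesion averaging the plan's 80% can survive. That also stands, so 69% should always carry its condition. The SD of 0.227 in VII.4 should not be counted as independent support either: its closeness to 0.23, and of N = 35 to N = 36, leaves open that both come from one source.

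Fourth, the plan already concedes that 0.03, 0.107 and 0.117 are below its limit. It does, and tissue-specific limits leave that concession unchanged.

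A reader might also infer that the study is underpowered for its main question. The documents do not support this. The primary endpoint asks whether "mpMR parameters measured after 2 months of neoadjuvant ADT therapy (TP1) correlate with nadir PSA post 8-weeks of ADT", together with a comparison of responders and non-responders. Those are sized in VII.1 and VII.4, and neither uses the averaged SD.

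**Conclusion.** The point holds as a minor one about a mis-applied input. One limit of 0.14 is held against two tissues and is the limit for neither. On the quoted SDs it should be about 0.16 in tumor (0.13 to 0.20) and about 0.12 in healthy tissue (0.08 to 0.22).

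This rests on three assumptions: the SDs are those of the within-patient change (VII.2 calls the result an SD for ADC, but a paired calculation needs the SD of the change); they are patient-level; and, for the tumor range, the 36 observations are independent. Under the per-lesion assumption, tumor power at 0.14 is 69% to 93%.

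The mismatch between -0.29 and 2.8% is a secondary source query. A reader might infer a decimal slip or figures taken from the wrong study. The documents cannot settle that: VII.2 does not say what the percentage is relative to, and the baseline of 1.006 belongs to another study. The change itself does not enter the power calculation. It matters only for interpretation, because -0.29 is the only tumor-labelled change in VII.2 above the limit.

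**What to change.** In VII.2, replace the single limit with two, for example: With 30 subjects and two-sided alpha 0.05/6, 80% power corresponds to a within-patient ADC change of about 0.16 in tumor (0.13 to 0.20 over the 95% interval of the SD, if the 36 observations are independent) and about 0.12 in healthy tissue (0.08 to 0.22), taking the published SDs as patient-level SDs of change.

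State that the SD is that of the within-patient change, whether it is per patient or per lesion, and whether a patient contributes one lesion or a mean. Name the tissue for 0.107 and 0.117.

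Before finalizing, check -0.29, 2.8%, N = 36 and the SDs against the cited source. If an SD changes, the limit is 0.676 times the corrected patient-level value. If the tumor change proves to be about 0.03, add that a non-significant tumor result would not rule out a change of that size.

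The cost is a source check and a few sentences. Sample size, tests and conduct stay as they are; the only downside is a slightly less favorable tumor limit.

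### The 80% power in VII.3 for a tumor-normal ADC difference of 0.19 rests on the SD of a change over time; the SD that the comparison needs is not in the documents

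*Combined protocol and SAP*

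**What the plan says.** Section VII.2 (Within-Patient ADC Changes) draws its variability from a cited radiotherapy imaging study, which "reported a change in ADC between six weeks RT and baseline of -0.29 in tumor". The corresponding change for healthy tissue is given as -0.56. The two changes are reported "with SDs of 0.23 and 0.18, respectively" (units of 10^-3 mm²/s). The section continues: "Using the average variance above, we estimate a SD for ADC of 0.20". That value feeds a paired t-test between two time points, corrected for 6 pairs of time points, with a detectable difference of 0.14.

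Section VII.3 (Comparison of Normal Tissue ADC With Tumor) then says that "with 30 subjects we expect 80% power to detect an absolute difference in mean ADC of 0.19 or greater". The method behind this claim is given only in outline, as "based on a two-tailed two-sample t-test, adjusted for multiple comparison of time-points". The section states neither an SD nor a divisor. Its benchmark is a published mean tumor-healthy difference of 0.20.

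Section VI and its Prostate MRI subsection give four scans: baseline, TP1, TP2 and TP3.

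**The concern.** The two sections ask different questions. VII.2 asks whether ADC moves within a man between two scans, and an SD of change is the right kind of SD for that. VII.3 asks whether ADC differs between two tissues at a scan. A two-sample test of that question needs the SD of ADC level within each tissue. A within-man test needs the SD of the tumor-minus-normal difference. An SD of change over time is neither of these, and once it has been relabelled as an SD for ADC the mismatch is easy to miss.

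What is at stake is the reassurance VII.3 offers: the detectable 0.19 lies just below the published 0.20. With so thin a margin, a modest error in the SD decides whether the claim stands.

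**Working it through.** **Inputs.** From VII.2: change SDs 0.23 (tumor) and 0.18 (healthy), two-tailed alpha 0.05, 6 pairs of time points. From VII.3: 30 subjects, 80% power, detectable difference 0.19, benchmark 0.20. From section VI: 4 scans. All power figures use the noncentral t distribution, with Bonferroni alpha 0.05/k.

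**1. Reproduce the plan's figures.**
- Averaged SD = sqrt((0.23² + 0.18²)/2) = sqrt((0.0529 + 0.0324)/2) = 0.2065.
- VII.2, paired, n = 30, k = 6: the standardized detectable difference is 0.6763, and 0.6763 × 0.2065 = 0.140. This matches the stated 0.14.
- VII.3, two-sample, 30 v 30, k = 6: the standardized difference is 0.9264, and 0.9264 × 0.2065 = 0.191. This matches the stated 0.19. With the rounded SD, 0.9264 × 0.20 = 0.185, which also rounds to 0.19.
- VII.3 with k = 4: the standardized difference is 0.8862, giving 0.183 (SD 0.2065) or 0.177 (SD 0.20). Both round to 0.18.

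One SD and one divisor therefore account for both stated figures.

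**2. How large a level SD can the two-sample claim tolerate?** The largest SD with 80% power at 0.20 is 0.20 divided by the standardized difference.
- k = 6: 0.20/0.9264 = 0.216, and 0.216/0.2065 = 1.05.
- k = 4: 0.20/0.8862 = 0.226, and 0.226/0.2065 = 1.09.

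**3. What the change SD implies about the level SD.** The documents give no between-scan correlation rho, so it is assumed over a range. With equal variance at both scans (also an assumption), level SD = 0.2065/sqrt(2(1 - rho)). Two-sample test, k = 4:

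| rho (assumed) | Level SD | Detectable difference | Power at 0.20 |
|---|---|---|---|
| 0.25 | 0.169 | 0.15 | 98% |
| 0.5 | 0.207 | 0.18 | 88% |
| 0.7 | 0.267 | 0.24 | 63% |
| 0.8 | 0.327 | 0.29 | 42% |

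Under this assumption the change SD equals the level SD only at rho = 0.5. Power at 0.20 drops below 80% above rho of about 0.54 (k = 6) or 0.58 (k = 4).

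**4. The paired version.** Assume one tumor and one normal value per man at each scan. The SD of the difference that gives 80% power at 0.20 is at most:
- k = 6: 0.20/0.6763 = 0.296.
- k = 4: 0.20/0.6447 = 0.310.

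If the level SD is the same in both tissues and r is the tumor-normal correlation within a man (assumed), the difference SD is level SD × sqrt(2(1 - r)). Paired power at 0.20, k = 4:

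| Level SD | r = 0 | r = 0.3 | r = 0.5 |
|---|---|---|---|
| 0.267 | 60% | 78% | 92% |
| 0.327 | 40% | 57% | 75% |

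**The case against.** The strongest reply is that nothing here shows the study to be underpowered. The direction of the error is unknown: at assumed between-scan correlations of 0.25 and 0.5, power at 0.20 is 98% and 88%, which bears the plan out. The low figures need a high between-scan correlation and a test that ignores the pairing of tissues within men. A paired analysis can recover much of the loss. All of this stands.

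One could also read VII.3 as comparing changes between tissues, in which case an SD of change and 6 comparisons would both fit. The text points the other way. The heading and the wording refer to mean ADC, the benchmark is a difference in level, and VII.2 and VII.4 name changes when they mean them.

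A reader might infer that 6 comparisons instead of 4 is a second error that undermines the power. The documents do not support that. VII.3 states no divisor, so 6 is a back-calculation. It is also the stricter choice: moving to 4 lowers the detectable difference from 0.191 to 0.183 and raises power at 0.20 from 84% to 88% (SD 0.2065).

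Nor can it be said that 0.19 arises only from SD 0.2065. SD 0.20 with 6 tests also rounds to it, and SD 0.20 with 8 tests gives 0.191. Reuse of the VII.2 inputs is the likeliest explanation, not a proven one.

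Finally, tumor versus normal tissue is not an endpoint in section III, and VII.1 treats the power for the primary correlation separately. That limits the consequence.

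**Conclusion.** The point holds in this form: the only SD available to VII.3 describes a within-patient change over time, and the documents give neither the SD of ADC level nor the SD of the within-man tumor-normal difference. The claim of 80% power at 0.19 is therefore unsupported, and true power could be higher or lower. The calculation itself reproduces; the fault is the kind of SD fed into it.

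The margin is thin for the two-sample test as written, where a level SD 5% (6 tests) to 9% (4 tests) above 0.2065 takes power at 0.20 below 80%. The range of 98% down to 42% rests on assumed between-scan correlations of 0.25 to 0.8, equal variances, 4 tests and independence of the two tissues. It should not be read as a finding that the comparison is underpowered. The unstated divisor is a secondary matter of consistency. The paragraph should be corrected because it states a power figure on the wrong input, but it does not bear on the primary endpoint.

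**What to change.** In VII.2, label the 0.20 as the SD of change in ADC.

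In VII.3:
- Specify a paired tumor-normal test at each scan.
- State the SD of the within-man difference and its source, either the cited study or this study's own baseline scans. If the two-sample test is kept, state the SD of ADC level within tissue instead.
- State the multiplicity divisor. One test at each of four scans gives 4; keeping 6 is conservative but should be said.
- Replace the single 0.19 with detectable differences over a range of SDs. At alpha 0.05/4 and 80% power:

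| SD | Two-sample, SD of level (0.8862 × SD) | Paired, SD of difference (0.6447 × SD) |
|---|---|---|
| 0.15 | 0.13 | 0.10 |
| 0.20 | 0.18 | 0.13 |
| 0.25 | 0.22 | 0.16 |
| 0.30 | 0.27 | 0.19 |
| 0.35 | 0.31 | 0.23 |

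The cost is one rewritten paragraph and one relabelled figure. The stated detectable difference may become less favourable. No patients or scans are added.
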